4.2.1. Subgroups

- 1) Chronic pain:
 - a. Full analysis set for participants with chronic pain
 - b. Full analysis set for participants without chronic pain

Participants with chronic pain are defined to have at least one of following criteria during pre-Oxbryta or post-Oxbryta:

- SCD complications page: Avascular Necrosis, Chronic Pain; OR
- Non-SCD medical history page: Arthralgia, Arthritis, Neuralgia, Osteoarthritis, Osteonecrosis, Osteoarthritis, Rheumatoid arthritis, Spinal osteoarthritis; OR
- Concomitant medications page: BACLOFEN, GABAPENTIN, MELOXICAM, PREGABALIN, all “BUPRENORPHINE”, DULOXETINE, DULOXETINE HYDROCHLORIDE, METHADONE, METHADONE HYDROCHLORIDE, PREGABALIN.

- 2) Maximum increase from Pre-Oxbryta in Hb
 - a. Full analysis set for participants with > 1 g/dL maximum increase from Pre-Oxbryta in Hb during the study period

b. Full analysis set for participants with ≤ 1 g/dL maximum increase from Pre-Oxbryta in Hb during the study period

3) Full analysis set where participants had a non-missing Pre-Oxbryta SCD complication will be included in the analysis.

4) Full analysis set where participants who had a non-missing Pre-Oxbryta SCD complication or participants who had an adverse event reported in Pre-Oxbryta or Post-Oxbryta will be included in the analysis.

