4.7.3. Analyses for Effectiveness Endpoint Measures

Since this study was not designed as the efficacy study for different indications that contribute significant information about product safety, the analyses in the SAP are considered fit-for-purpose for an abbreviated clinical study report with data scope including 1) full safety data and 2) limited efficacy data to support the benefit-risk evaluation.

Given the reporting nature of the PROMIS items, the reported PRO response was sparse. Therefore, they were excluded from the planned CSR analyses.

The analyses for effectiveness endpoints are based on full analysis set (Section 4.2). The analyses for the abbreviated CSR focus on hematologic and renal function laboratory parameters and SCD-related clinical events.

Participant disposition, non-SCD medical history, concomitant medication, study drug administration (including dosage changes initiated by the participant and by the physician), demographics and baseline characteristics will be summarized descriptively based on full analysis set.

The descriptive statistics will be provided for the following medications:

- long-acting opioids
- Erythropoiesis-stimulating agents
- Other relevant pain meds (e.g. Gabapentin, Lyrica, Cymbalta)
- SCD disease modification agents (hydroxyurea, Adakveo/crizanlizumab, L-Glutamide/levoglutamide).

The study drug administration will be categorized as 1) < 1 month, 2) >=1, <2 months, 3) < 3 months, 4) >=3 months, < 6 months, 5) >=6 months, < 9 months, 6) >=9 months, < 12

months, 7) ≥ 12 months, < 18 months, 8) ≥ 18 months, < 24 months, 9) ≥ 24 months, < 36 months, 10) ≥ 36 months, < 48 months and 11) ≥ 48 months.

The following effectiveness endpoints will be summarized descriptively:

- Change from pre-Oxbryta treatment period in the following hematologic parameters corresponding to treatment with Oxbryta® (Voxelotol):
 - Hb
 - Hemolysis measures, including % reticulocytes, absolute reticulocytes, bilirubin (total, direct, and indirect)
 - ALT and AST

Analysis: Observed and change from pre-Oxbryta treatment period on Hb, Hemolysis measures will be summarized descriptively ([Section 4.7](#)) by visit

If a queried hemolysis value remained greater than its threshold listed in the table below, the value would be deemed erroneous and excluded from the analysis,

Parameter	Threshold
Reticulocyte Count (absolute)	10,000 $10^{9}/L$
Ferritin	100,000 $\mu g/L$

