4.7.5. Subgroup analyses

Analysis: The annualized incidence rate (per patient year) of rate of ‘Acute Pain Crisis’ (SCD Complications) will be performed by Pre-Oxbryta and Post-Oxbryta.

Analysis subgroups:

- Chronic pain
 - a. participants with chronic pain
 - b. participants without chronic pain
- Maximum increase from Pre-Oxbryta in Hb
 - a. Full analysis set for participants with > 1 g/dL maximum increase from Pre-Oxbryta in Hb
 - b. Full analysis set for participants with <= 1 g/dL maximum increase from Pre-Oxbryta in Hb

Analysis: Annualized incidence VOC rate for pre-Oxbryta and post-Oxbryta will be reported.

The VOC event for Pre-Oxbryta is defined as 1) SCD complication with ‘Acute Pain Crisis’ in the Pre-Oxbryta SCD complication page or 2) any qualifying complications from SCD AE prior to Treatment Start Date.

The VOC event for Post-Oxbryta is defined as any qualifying complications from SCD AE on or after the treatment start date.

The qualifying complications from SCD AE are those that met at least one of the following two conditions:

- AE preferred term (AEDECOD) to be 'Sickle cell anaemia crisis';
- type of complications (CMPTYP) is 'Acute Pain Crisis'

- 1) Analysis population: Safety analysis set where participants had a non-missing Pre-Oxbryta SCD complications will be included in the analysis.
- 2) Analysis population: Safety analysis set where participants who had a non-missing Pre-Oxbryta SCD complications or participants who had an adverse events reported in Pre-Oxbryta or Post-Oxbryta will be included in the analysis.

Analysis: The annualized VOC incidence rate (per patient year) will be performed by Pre-Oxbryta and Post-Oxbryta.

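### The closed term lists that define chronic pain can leave some participants with chronic pain in the 'without chronic pain' subgroup

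*SAP*

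**What the plan says.** SAP 4.2.1 sets the rule: "Participants with chronic pain are defined to have at least one of following criteria during pre-Oxbryta or post-Oxbryta". The three criteria are:

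- SCD complications: "SCD complications page: Avascular Necrosis, Chronic Pain; OR"
- Medical history: "Non-SCD medical history page: Arthralgia, Arthritis, Neuralgia, Osteoarthritis, Osteonecrosis, Osteoarthritis, Rheumatoid arthritis, Spinal osteoarthritis"
- Concomitant medications: "BACLOFEN, GABAPENTIN, MELOXICAM, PREGABALIN, all “BUPRENORPHINE”, DULOXETINE, DULOXETINE HYDROCHLORIDE, METHADONE, METHADONE HYDROCHLORIDE, PREGABALIN"

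The lists carry no 'for example' or 'including' wording. The only class-type entry is the one covering all buprenorphine. A participant who matches nothing falls into the group that SAP 4.7.5 calls "participants without chronic pain". SAP 4.7.5 plans an annualized acute pain crisis rate, before and after the first dose, in each subgroup. SAP Appendix A reports these as Tables 15.5.1 (with) and 15.5.2 (without).

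Two other places bear on the lists. SAP 4.7.3 names "long-acting opioids" first among the medication groups to be summarised, followed later by other pain medications with gabapentin, Lyrica and Cymbalta as examples. Protocol 10.3.6.1.8 collects chronic/acute pain and avascular necrosis as SCD complications, and Protocol 10.3.6.1.10 collects opioids in daily morphine equivalents.

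**The concern.** With a closed list, what is omitted counts as absence of the condition. Two omissions stand out. The diagnosis being defined, chronic pain, does not qualify when it is recorded on the non-SCD medical history page. And of the long-acting opioids, which the SAP elsewhere treats as a class of interest, only methadone and buprenorphine count. Meanwhile the rule accepts much weaker evidence: a single record of meloxicam, baclofen or arthralgia is enough.

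At stake is what the label on Table 15.5.2 means. If participants with chronic pain sit in that table, and if they have more crises, the reported rate is too high for the population the title describes.

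**Working it through.** The plan gives no chronic-pain prevalence, miss rate or expected crisis rate, so there is no figure of its own to reproduce. The check has two parts: applying the rule as written, and an illustration on assumed inputs.

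**Counting the lists**

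- SCD complications page: 2 terms, one of them Chronic Pain.
- Medical history page: 8 entries, 7 distinct (osteoarthritis twice), none containing 'chronic'.
- Medications page: 10 entries, 9 distinct (pregabalin twice). The opioids are methadone (two entries) and buprenorphine.

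**Applying the rule literally, with no other qualifying record**

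| Only record | Subgroup |
|---|---|
| Chronic pain, SCD complications page | with |
| Chronic pain, non-SCD medical history page | without |
| Long-acting opioid other than methadone or buprenorphine | without |
| Any meloxicam or baclofen record | with |
| Arthralgia, medical history page | with |

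**Comparing with the rest of the SAP**

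All three examples of other pain medications in SAP 4.7.3 are in the rule, as gabapentin, pregabalin (Lyrica) and duloxetine (Cymbalta). The long-acting opioid group is represented by two drugs only, and no reason is given. The rule also takes a bone-necrosis term from either page (avascular necrosis on one, osteonecrosis on the other). It does not do the same for chronic pain.

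**Illustration of size (all inputs assumed except the enrolment target of about 500)**

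Let p be the true prevalence of chronic pain, q the share of true cases missed by all three pages, and RR the true crisis-rate ratio, with versus without. Assume no false positives.

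- Share of true cases in the 'without' group: m = pq / (pq + 1 - p)
- Inflation of its rate: 1 + m(RR - 1)
- Observed ratio: RR / [1 + m(RR - 1)]

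For p = 0.5, q = 0.3, RR = 2: m = 0.15 / 0.65 = 0.231, inflation 1.231, observed ratio 2 / 1.231 = 1.62.

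| p | q | Missed of 500 | m | Inflation (RR 2) | Observed ratio |
|---|---|---|---|---|---|
| any | 0 | 0 | 0% | 1.000 | 2.00 |
| 20% | 10% | 10 | 2.4% | 1.024 | 1.95 |
| 30% | 10% | 15 | 4.1% | 1.041 | 1.92 |
| 30% | 20% | 30 | 7.9% | 1.079 | 1.85 |
| 50% | 10% | 25 | 9.1% | 1.091 | 1.83 |
| 50% | 30% | 75 | 23.1% | 1.231 | 1.62 |

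In the last row, RR = 1.5 gives an inflation of 1.115 and RR = 3 gives 1.462.

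**Effect on the post/pre ratio**

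The flag is fixed per participant. Suppose missed participants share the true post/pre ratio θ, and contribute shares m_pre and m_post of the 'without' group's person-time. The observed ratio is then θ × [1 + m_post(RR - 1)] / [1 + m_pre(RR - 1)]. With equal shares it is exactly θ. With RR = 2, and shares of 4.1% before and 2.4% after (two values from the table, chosen only to show the scale), the factor is 1.024 / 1.041 = 0.984, a shift of 1.6%. If missed participants had a different θ, the ratio would move towards theirs in proportion to their share of events.

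**The case against.** The strongest reply is that the rule is an OR and its first criterion is the right place for this diagnosis. In an SCD registry, chronic pain belongs on the complications page, where it qualifies. The other page is for non-SCD history. Only a participant recorded nowhere else is misplaced, and nothing shows that one exists. This stands as to size. It does not show that the complications page is complete: Protocol 9.7 lets sites leave fields blank when an assessment is not done as standard of care, and SAP 4.2.1 itself defines a subgroup restricted to participants with a non-missing pre-treatment complication, so it allows for participants without one. The other two lists matter most for them.

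Second, SAP 4.7.3 asks for a descriptive medication summary and does not say that long-acting opioids identify chronic pain. That is correct, so the two sections sit badly together without contradicting each other. Opioid use is also a proxy, and Protocol 10.3.6.1.3 defines a crisis partly by narcotic treatment, so a broad opioid criterion would risk selecting on the outcome's own treatment. This is a good reason to confine any addition to long-acting products. It does not explain why weaker proxies are accepted.

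Third, the listed salt forms suggest that the lists may have been built from recorded terms, in which case an unlisted drug may simply not occur. The documents do not say so. If it is true, the fix changes nothing, and the SAP could state it.

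Fourth, SAP 4.7.5 specifies no with-versus-without contrast; the rates are descriptive and compared before and after within each subgroup. This stands: the exposed quantity is mainly the rate level in Table 15.5.2.

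**Conclusion.** The point holds as a conditional one. Followed literally, the rule labels a participant with a recorded diagnosis of chronic pain as 'without chronic pain' when that diagnosis appears only on the non-SCD medical history page, and does the same for chronic pain evident only through an unlisted long-acting opioid.

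A reader might infer more: that participants with chronic pain are generally analysed as being without it, or that the rate in Table 15.5.2 is inflated by a known amount. The documents support neither. Most SCD chronic pain should be caught by the first criterion, and every figure above depends on assumed p, q and RR. The effect is zero at q = 0. If crisis rates are higher with chronic pain, missed cases raise the level of the 'without' rate, by 0 to 23% over the assumed range with RR = 2. The post/pre ratio may change little.

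The rule can also err the other way, by counting incidental meloxicam, baclofen or arthralgia records as chronic pain. If those participants otherwise resemble the 'without' group, they lower the rate in Table 15.5.1 and do not offset the effect on Table 15.5.2.

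The repeated osteoarthritis and pregabalin entries have no effect under an OR rule.

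**What to change.** In SAP 4.2.1:

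1. Add 'Chronic pain' to the non-SCD medical history list.
2. Add long-acting opioids as identified for the SAP 4.7.3 summary. Restrict this to long-acting products, so that opioids given for acute crises do not define the subgroup.
3. Apply the revised flag to Tables 15.5.1 and 15.5.2. At minimum, report it as a sensitivity definition beside the current one, with the number of participants who change group.

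The cost is SAP wording and a code list. The documents do not show that list, but the SAP 4.7.3 summary cannot be produced without some way of identifying these drugs. The 'without' group becomes somewhat smaller, and some participants will be classified on a proxy. Removing the duplicate entries is clerical. Adding avascular necrosis to the history page would be largely redundant, because osteonecrosis is already listed there.

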9.4. Variables

| Variable | Role | Data source(s) | Operational definition |
|-------------------------------|--|------------------|--|
| Index date | Study period | Case report form | Inform consent date |
| Index year | Study period | Case report form | Inform consent date |
| Pre-Oxbryta | Study period | Case report form | Baseline: the most recent observation before receiving Oxbryta |
| Post-Oxbryta | Study period | Case report form | Follow up period up to 5 years |
| End of Treatment | Study period | Case report form | Captured from end of treatment form |
| End of Study | Study period | Case report form | Captured from end of study form |
| Age | Demographics | Case report form | Age at index year |
| Sex | Demographics | Case report form | Captured from the inform consent and eligibility form |
| Race/Ethnicity | Demographics | Case report form | Captured from the inform consent and eligibility form |
| SCD genotype | SCD disease history | Case report form | Captured from SCD disease history form |
| Hydroxyurea use | SCD disease history | Case report form | Captured from SCD disease history form |
| Height | Baseline characteristics | Case report form | Captured from Physical examination form |
| Weight | Baseline characteristics | Case report form | Captured from Physical examination form |
| Pre-Oxbryta SCD complications | Medical history | Case report form | Captured from Pre-Oxbryta treatment form |
| Concomitant Medications | Concomitant Medications | Case report form | Captured from concomitant medications form |
| Hemoglobin | Effectiveness endpoint measures - Hematology | Case report form | Captured from laboratory assessment-Hematology form |
| Reticulocyte count (%) | Effectiveness endpoint measures – Hematology | Case report form | Captured from laboratory assessment-Hematology form |
| Reticulocyte count | Effectiveness endpoint | Case report form | Captured from laboratory |

| Variable | Role | Data source(s) | Operational definition |
|--|--|------------------|---|
| (absolute) | measures – Hematology | | assessment-Hematology form |
| White blood cells (WBC) | Effectiveness endpoint measures – Hematology | Case report form | Captured from laboratory assessment-Hematology form |
| Absolute neutrophil count (ANC) | Effectiveness endpoint measures – Hematology | Case report form | Captured from laboratory assessment-Hematology form |

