10.3.6. Effectiveness Data

10.3.6.1. Clinical Outcomes

10.3.6.1.1. Laboratory Assessments

The following data will be recorded on the CRF:

For pre-Oxbryta® (Voxelotor) Treatment Visits, only the most recent results from regularly scheduled outpatient visit will be entered.

For post-Oxbryta® (Voxelotor) Treatment Regularly Scheduled Outpatient Visits, all available results during the data collection period will be entered.

For post-Oxbryta® (Voxelotor) Acute Visits (Emergency Department, Hospitalization, Acute Pain/Infusion Center), only the results on the day of presentation (or first available results during the visit) and day of discharge will be entered, if available.

The following data from the most recent results will be recorded in the CRF:

- Hb (including % HbF at baseline and all follow up visits), white blood cells (WBC), absolute neutrophil count (ANC), mean corpuscular volume (MCV), mean corpuscular hemoglobin concentration (MCHC), Platelets, aspartate aminotransferase (AST), alanine aminotransferase (ALT), and lactate dehydrogenase (LDH).
- Hemolysis measures, including % reticulocytes, absolute reticulocytes, bilirubin (total, direct, and indirect)
- Measures of iron overload (ferritin, iron, TIBC, T2*MRI)
- Creatinine (Serum)
- Albuminuria (urine albumin/creatinine ratio [ACR])
- Hemoglobinuria (urine dipstick positive for blood +1 or greater and ≤ 2 RBC by high power field)
- Serum cystatin C
- eGFR calculated using CKD-EPI equation

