4.3. Variables

Variable	Role	Data source(s)	Operational definition
Index date	Study period	Case report form	Inform consent date
Index year	Study period	Case report form	Inform consent date
Pre-Oxbryta	Study period	Case report form	Baseline: any assessments within 12 months before receiving first dose of Oxbryta® (Voxelotor)
Post-Oxbryta	Study period	Case report form	Follow-up period for up to 5 years after the first dose of Oxbryta® (Voxelotor)
End of Treatment	Study period	Case report form	Captured from end of treatment form
End of Study	Study period	Case report form	Captured from end of study form
Age	Demographics	Case report form	Age at first dose of Oxbryta
Sex	Demographics	Case report form	Captured from the inform consent and eligibility form
Race/Ethnicity	Demographics	Case report form	Captured from the inform consent and eligibility form

SCD genotype	SCD disease history	Case report form	Captured from SCD disease history form
Hydroxyurea use	SCD disease history	Case report form	Captured from SCD disease history form
Height	Baseline characteristics	Case report form	Captured from Physical examination form
Weight	Baseline characteristics	Case report form	Captured from Physical examination form
Pre-Oxbryta SCD complications	Medical history	Case report form	Captured from Pre-Oxbryta treatment form
Concomitant Medications	Concomitant Medications	Case report form	Captured from concomitant medications form
Hemoglobin	Effectiveness endpoint measures - Hematology	Case report form	Captured from laboratory assessment-Hematology form
Reticulocyte count (%)	Effectiveness endpoint measures - Hematology	Case report form	Captured from laboratory assessment-Hematology form
Reticulocyte count (absolute)	Effectiveness endpoint measures - Hematology	Case report form	Captured from laboratory assessment-Hematology form
White blood cells (WBC)	Effectiveness endpoint measures - Hematology	Case report form	Captured from laboratory assessment-Hematology form
Aspartate Aminotransferase (AST)	Effectiveness endpoint measures - Hematology	Case report form	Captured from laboratory assessment-Hematology form
Alanine Aminotransferase (ALT)	Effectiveness endpoint measures - Hematology	Case report form	Captured from laboratory assessment-Hematology form
Bilirubin (Total)	Effectiveness endpoint measures - Chemistry	Case report form	Captured from laboratory assessment-Chemistry form

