4.7.1. Index date and follow-up

The index date is defined as the inform consent date. The Post Oxbryta period is from the first dose of Oxbryta to the date of end of treatment or end of study.

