4.7.4. Safety analysis

SCD complications are defined as 'Yes' to the question 'is this a SCD Complication' in the SCD complications/AE form while the other AEs are defined as 'No' to the question 'is this a SCD Complication' in the SCD complications/AE form.

All safety analyses will be based on safety analysis set (Section 4.2). The analysis period for Pre-Oxbryta is 12 months before the first dose of Oxbryta and the analysis period for post-Oxbryta is from the first dose of Oxbryta through end of the study or the date of dose pausing or treatment discontinuation if the date of end of study date is missing.

SAEs and protocol-specified AEs will be classified according to the Medical Dictionary for Regulatory Activities (MedDRA). The frequency of SCD complications and other AEs treatment-emergent adverse events (TEAEs) and treatment emergent SAEs will be tabulated by system organ class, preferred term, severity (and total), and relationship to Oxbryta® (Voxelotor) treatment. The pregnancy outcomes and fertility will be reported as a listing. Any events (including deaths) leading to discontinuation of the study and SAEs will be listed.

A TEAE is defined as an AE that occurs during the effective duration of treatment defined as the time from the first dose of Oxbryta through end of treatment date or the end of study completion/discontinuation date (if the date of end of treatment is missing) +28 days.

On the AE case report form there is a question “Did AE start prior to first dose?”

- If the response is “Yes” or the adverse event start date is missing, and the end date is prior to the first dose of Oxbryta, then the AE is not considered a TEAE
- If the response is “No” or “Unknown”, then the AE is considered a TEAE

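### The Hb-rise subgroup takes the maximum Hb at any time in the study, with no limit by visit type, transfusion or treatment status, so the crises counted in each group can help decide who is in it.

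*SAP*

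**What the plan says.** **Subgroup rule.** SAP 4.2.1 splits participants at 1 g/dL. The upper arm is "Full analysis set for participants with > 1 g/dL maximum increase from Pre-Oxbryta in Hb during the study period", and the lower arm is its complement. SAP 4.7.5 repeats the cut without a time window and asks for annualized acute pain crisis rates pre- and post-Oxbryta. These appear as Tables 15.5.3 and 15.5.4.

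**Which Hb values exist.** Protocol 10.3.6.1.1 treats the two periods differently. Before dosing, "only the most recent results from regularly scheduled outpatient visit will be entered". After dosing, all scheduled outpatient results are entered. For emergency, inpatient and acute pain or infusion visits, "only the results on the day of presentation (or first available results during the visit) and day of discharge will be entered", if available. The same section also says "The following data from the most recent results will be recorded in the CRF", without saying how that fits the other rules.

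**Baseline.** Protocol 9.4 has "Baseline: the most recent observation before receiving Oxbryta". SAP 4.3 has "Baseline: any assessments within 12 months before receiving first dose of" Oxbryta.

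**End of the post-dose period.** SAP 4.7.1: "The Post Oxbryta period is from the first dose of Oxbryta to the date of end of treatment or end of study". SAP 4.7 takes patient-years from this definition. SAP 4.7.4 runs "from the first dose of Oxbryta through end of the study or the date of dose pausing or treatment discontinuation", the last two applying only if the end-of-study date is missing. SAP 4.2.1 refers only to the study period. Protocol 10.4.1.2 keeps following people who stop the drug, up to 5 years from first dose.

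**Purpose.** SAP 4.5 gives the relation between Hb change and clinical events as what the sample of about 500 is meant to estimate, with no formal calculation.

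**The concern.** A maximum grows with the number of values it is taken over. If acute-visit values count, each post-dose crisis can add up to two Hb values, and a discharge value may follow a transfusion. People with more post-dose crises are then more likely to land in the >1 g/dL group, where those crises are counted. The <=1 g/dL group is partly selected for having few post-dose crises, so its rate can fall from pre to post with an inert drug.

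The baseline has no matching feature, because only a scheduled value is entered. Values taken after stopping the drug, or soon after any transfusion, may also count as a rise from Pre-Oxbryta.

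Tables 15.5.3 and 15.5.4 are the only outputs in Appendix A that relate Hb change to crises. They belong to the limited efficacy data that SAP 4.7.3 says will support the benefit-risk evaluation. They are descriptive, so what is at stake is interpretation, not type I error.

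**Working it through.** The plan states no figure to reproduce. SAP 4.2.1, 4.3, 4.7.1, 4.7.3 and 4.7.5 contain no Hb restriction by visit type, transfusion or treatment. The only numeric lab exclusions, in 4.7.3, are for absolute reticulocytes and ferritin.

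**Step 1: noise in a maximum.** Assume no true Hb change, one baseline value, k follow-up values and independent normal within-person variation with SD s (assumed 0.5 or 0.7 g/dL). Then

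P(max - baseline > 1) = integral of phi(b) x [1 - Phi(b + 1/s)^k] db.

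The schedule of activities gives k = 4 collection points to month 12 and k = 12 to month 60.

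| k | s = 0.5 | s = 0.7 |
|---|---|---|
| 4 | 21% | 37% |
| 12 | 37% | 57% |

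For k = 1 and s = 0.5 the chance is 8%. If 12 crises each add two values with no Hb dip, k = 12 + 2 x 12 = 36, and the chance at s = 0.5 rises from 37% to 54%. So both longer follow-up and more crises raise the chance of entering the upper group.

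**Step 2: effect on crisis rates.** Simulation; all inputs are assumed unless marked.
- Crises: gamma-Poisson, mean 2 per year, shape 1.
- Periods: 12 months pre-dose (SAP 4.7.4); follow-up uniform from 0.5 to 5 years.
- Hb: one scheduled value per collection month (schedule of activities), and two values per crisis with labs.
- Transfusion: a +1.5 g/dL value at the stated share of crises with labs.

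Results are post/pre crisis-rate ratios. Ranges cover both SDs and separate runs of the model.

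| Setting | >1 g/dL | <=1 g/dL |
|---|---|---|
| No effect; labs at every crisis, no dip, 10% transfused | about 1.02 | 0.86-0.88 |
| No effect; labs at half, acute Hb 0.5 low, 5% transfused | 1.01-1.03 | 0.96-0.98 |
| No effect; acute Hb 0.5 low, no transfusion | 1.00-1.01 | 0.98-1.00 |
| No effect; scheduled values only | 1.00 | 1.00 |
| Real relation, true values | 0.80 | 1.00 |
| Real; SAP rule, every crisis, 10% | about 0.90 | about 0.86 |
| Real; SAP rule, half, 5% | 0.87-0.89 | 0.92-0.97 |
| Real; scheduled values only | 0.85-0.87 | 0.97-0.99 |

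The real relation assumes that half of participants gain 1.2 g/dL and have 20% fewer crises.

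One half-capture cell (s = 0.5) in full: the upper group goes from 2.34 to 2.40 per year (2.40/2.34 = 1.03), and the lower from 1.83 to 1.76 (1.76/1.83 = 0.96).

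The near-nil third row depends on the assumed dip. Without it and with labs at every crisis, a modest gap remains. With five years of follow-up for everyone and s = 0.5 it is 2.31/2.28 = 1.01 against 1.68/1.71 = 0.98, and it is wider when follow-up is shorter. In that run the post-dose levels alone, 2.31 against 1.68, differ clearly although the true mean rate is 2 throughout.

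**Step 3: what the restriction does not cure.** Suppose low baseline Hb goes with more pre-dose crises: baseline lowered by 0.5 x min(pre-dose crises, 4)/4 g/dL, half capture, 0.5 dip, 5% transfused, no drug effect.

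| Rule | >1 g/dL | <=1 g/dL |
|---|---|---|
| SAP rule | 0.93-0.96 | 1.04-1.06 |
| Scheduled values only | 0.91-0.95 | 1.07-1.08 |
| Month-3 landmark | 0.89-0.92 | 1.03 |

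This is regression to the mean. It appears under every rule and is slightly larger with scheduled values only than under the SAP rule.

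**The case against.** **The documents do not say that acute values feed the maximum.** The protocol's line on most recent results and the by-visit Hb summary in SAP 4.7.3 could be read as narrowing the input. That is fair: the mechanism follows from the rule as written, not from a stated derivation. But nothing in the SAP excludes those values.

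**Labs at every crisis is unlikely.** The VOC definition in Protocol 10.3.6.1.3 includes crises handled by remote contact. Acute values are entered only if available, and Protocol 9.7 lets fields stay blank. This stands: the half-capture figures are more plausible, and they are small.

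**A reader might infer that the rule hides any real Hb-crisis relation.** The figures do not support that. Reversal needs full capture with 10% transfused. With half capture and 5% the relation is attenuated but keeps its direction, and scheduled values alone recover only about 0.11-0.13 (0.98 - 0.87 to 0.98 - 0.85) of the true 0.20 gap.

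**A reader might infer that the rule creates a false benefit for the drug.** That result comes from the assumed baseline link in step 3, not from acute or transfused values. The documents give no data on such a link.

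**The baseline wording conflict matters little for Hb.** With one scheduled pre-dose value entered, the two definitions usually coincide. Data brought over from the RETRO study (SAP 4.4) may be an exception.

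**The tables are descriptive, and Protocol 9.13 admits bias in comparisons.** True, but a general caveat does not tell a reader that the outcome can shape the groups.

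**Conclusion.** The point holds as a defect in a derivation rule. As written, the crises being counted can influence subgroup membership, and unequal follow-up adds misclassification by noise. SAP 4.7.1 and 4.7.4 also end the post-dose period differently, and 4.2.1 adopts neither.

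The size is uncertain. It ranges from close to nil (no transfusion, acute dip) through small (about 1.01-1.03 against 0.96-0.98) to material (about 1.02 against 0.86-0.88, with reversal of a real relation). Crisis rate, Hb variability, lab capture and transfusion share are all assumptions. Confidence is high for the missing rule and the mechanism, and moderate to low for the magnitude.

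This should be fixed before the tables are used. It does not show that the sponsor's results are biased in a known direction. How the chronic-pain subgroup is defined is a separate matter and forms no part of this conclusion.

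**What to change.** In SAP 4.2.1 and 4.7.5:

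1. Compute the maximum only from scheduled outpatient, on-treatment Hb values outside a stated window after a recorded RBC transfusion. Subtract the most recent scheduled pre-dose value, in line with Protocol 9.4 and 10.3.6.1.1.
2. Reconcile the end of the Post-Oxbryta period between SAP 4.7.1 and 4.7.4, and apply one end date to both the Hb maximum and the crisis count.
3. Report how many participants have no qualifying Hb, and show baseline Hb and pre-dose crisis rate by group.
4. State beside the tables that regression to the mean is not addressed and that the pre/post contrast by group is not a drug effect.
5. Optionally, add an early-landmark table as a sensitivity analysis: Hb change in a fixed early window, with crises and person-time counted after it.

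**Cost.** SAP wording and some reprogramming, with no new data collection. Visit type is already distinguished at data entry. Transfusion dates are assumed to be on the transfusions form, whose fields are not shown. Some participants will be unclassified, because labs are standard of care only. A month-3 landmark drops about 9% of post-dose crises in the model (0.25 year of a mean 2.75 years) and everyone without a value by then, so it should not be the main table.
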